CLINICAL PERFORMANCE STUDY PLAN

EuGeni SARS-CoV-2 Antigen Rapid Diagnostic Test

AnteoTech LTD.

Document reference number: █ Version 3.0

Date: 19-Sep-2022

CONFIDENTIAL

CONTACT INFORMATION

SPONSOR AND LEGAL MANUFACTURER

AnteoTech Ltd
[name]
[name]
[name]
[REDACTED]

AUTHORIZED REPRESENTATIVE IN EU:

MT Promedt Consulting GmbH
[name]
[name]
[REDACTED]
[REDACTED]

[figure not shown]
[figure not shown]
CRO:

AKRN Scientific Consulting
[REDACTED]
[REDACTED]
[REDACTED]

INVESTIGATIONAL SITE (S):

CONFIDENTIAL

CLINICAL PERFORMANCE STUDY PLAN (CPSP) SUMMARY

Version Number	3.0
Date	19-Sep-2022
Sponsor	
AnteoTech Ltd [name] [name] [name]   
 
EU authorized representative: MT Promedt Consulting GmbH [name] [name]  

Clinical Performance Study Name	EuGeni SARS-CoV-2 Antigen Rapid Diagnostic Test Clinical Performance Study
Clinical Performance Study Code	
Objectives	To determine the diagnostic accuracy in terms of specificity and sensitivity of the EuGeni SARS-CoV-2 Antigen Rapid Diagnostic Test in the diagnosis of SARS-CoV-2 in specimens prospectively collected by healthcare professionals from subjects suspected of COVID-19 disease or with unknown COVID-19 status.
Device Under Investigation	EuGeni SARS-CoV-2 Ag RDT assay and EuGeni Reader
Number of Required Specimens	
A minimum estimated of 1850 prospective specimens divided as follows:
 
Nasopharyngeal specimen collection:
 
 ○ 300 positive specimens from symptomatic subjects ○ 120 negative specimens from hospitalized patients ○ 505 negative specimens from subjects with respiratory symptoms 
Combined nasal mid-turbinate and throat specimen collection:
 
 ○ 300 positive specimens from symptomatic subjects ○ 120 negative specimens from hospitalized patients ○ 505 negative specimens from subjects with respiratory symptoms
Planned Number of Sites	Up to 10 sites in Europe
Study Design	This is a non-interventional, two-arm, prospective, non-randomized, open-label and multi-center Clinical Performance Study

CONFIDENTIAL

[figure not shown]
Primary Endpoints	
To assess the EuGeni SARS-CoV-2 Ag RDT diagnostic accuracy in terms of sensitivity and specificity measured as the following:
 
 • The diagnostic sensitivity will be assessed as the ability to identify the presence of a target marker associated with SARS-CoV-2, of nasopharyngeal specimens and combined nasal mid-turbinate and throat specimens, respectively, compared with gold-standard SARS-CoV-2 RT-PCR. • The diagnostic specificity will be assessed as the ability to recognise the absence of a target marker associated with SARS CoV-2, of nasopharyngeal specimens and combined nasal mid-turbinate and throat specimens, respectively, compared with gold-standard SARS-CoV-2 RT-PCR.
Secondary Endpoint	To compare the specificity and sensitivity rates of EuGeni SARS-CoV-2 Ag RDT between the two specimen collection methods.
Inclusion Criteria	
 1. Specimens from subjects over 12 years old agreeing to participate in the study and with a legal representative able to provide informed consent, OR; 2. Specimens from subjects over 18 years old able to provide informed consent. 3. Specimens collected with nasopharyngeal swabs, OR; 4. Combined nasal mid-turbinate and throat specimen collection.
Exclusion Criteria	
 1. Specimens and testing methods that are not deemed to be in line with gold-standard RT-PCR standards. 2. Specimens stored for over 2 hours at 2-8 °C temperature between collection and testing with EuGeni SARS-CoV-2 Ag RDT 3. Specimens stored for over 5 days at -20°C between collection and testing with RT-PCR. 4. Specimens stored for over 24h at 4°C between collection and testing with RT-PCR. 5. Contamination and/or deterioration of the specimen which, in the opinion of the investigator, may affect its handling and/or analysis. 6. The subject is deemed unsuitable to participate in the study by the investigator.
Coordinating Investigator	[REDACTED]
Electronic Data Capture (EDC)	[REDACTED]
Data Management & Biostatistics	[REDACTED]
Contract Research Organization (CRO)	AKRN Scientific Consulting S.L. (Madrid, Spain)
Expected Duration of the Study	[REDACTED]

CONFIDENTIAL

Investigational Site Name

CONFIDENTIAL

CONFIDENTIAL

CONFIDENTIAL

COMPLIANCE STATEMENT:

1. INTRODUCTION

Rapid antigen detection (RAD) tests are used to perform rapid diagnosis of SARS-CoV-2 infection based on a qualitative approach. RAD tests detect the viral antigen by the immobilized coated SARS-CoV-2 antibody placed on the device. The results of these tests are available in a short time, reducing the workload in diagnostic hospitals and laboratories and improving the turn-around time.

EuGeni SARS-CoV-2 Antigen Rapid Diagnostic Test is an *in vitro* Diagnostic (IVD) medical device intended to be used for the qualitative detection of SARS-CoV-2 nucleocapsid antigen. The result from this IVD test identifies the presence or absence of the SARS-CoV-2 antigen as an aid for the diagnosis of COVID-19 infection.

1.1 Background and rationale

In 2019 a novel corona virus, designated as SARS-CoV-2 and associated with unusual viral pneumonia named Corona virus Disease 19 (COVID-19), sprouted in the city of Wuhan, China, and rapidly spread to create a global pandemic. Identification of people infected with severe acute respiratory syndrome coronavirus 2 (SARS-CoV-2) is essential for controlling its spreading and public health management.

Since the beginning of the COVID-19 outbreak, tests that can enable both mass screening and reliable detection of infected people are needed¹. The reliance on testing underscores the importance of analytical sensitivity of virus assays, being the real-time quantitative polymerase chain reaction (RT-qPCR) from nasopharynx swab the gold-standard². However, RT-PCR is expensive, time-consuming, and requires specialized laboratory personnel and instrumentation compared to rapid tests³.

New developments in SARS-CoV-2 diagnostics have the potential to reduce cost and turnaround time⁴⁻⁶. Several diagnostic strategies are available for identifying or ruling out current infection, identifying people in need of care escalation, or testing for past infection and immune response. Point-of-care (POC) antigen and molecular tests for the detection of current SARS-CoV-2 infections are rapid antigen detection (RAD) tests, which allow earlier detection and isolation of confirmed cases compared to laboratory-based diagnostic methods.

Coronavirus RAD tests, have demonstrated good sensitivity and specificity in comparison to RT-qPCR⁷⁻⁹. Moreover, previous studies have shown that RADs can exhibit high sensitivity in detecting samples containing infectious virus, indicating a high sensitivity to detect contagious individuals^{10,11}.

The RAD tests, based on the immunochromatographic principle, detect SARS-CoV-2 nucleocapsid protein (N) at or near the place where a specimen is collected, providing results within few minutes³. In general, RAD tests consist of fixing match-paired antibodies to the surface of the cassette and coupling an anti-antigen match-paired antibodies to the detection nanoparticles.

[REDACTED]

[REDACTED]

[REDACTED]

[REDACTED]

[REDACTED]

EuGeni SARS-CoV-2 Ag RDT is a fluorescent immunochromatographic RAD test for COVID-19 rapid detection using the [REDACTED] for results interpretation. The [REDACTED] is expected to provide positive, negative, or invalid result for the presence of SARS-CoV-2 antigen. The EuGeni device is intended to be used by healthcare professionals only.

2. IN-VITRO DIAGNOSTIC MEDICAL DEVICE OVERVIEW

[figure not shown]
2.1 IVD Medical Device under investigation

The EuGeni SARS-CoV-2 Ag RDT is a test strip based on lateral flow technology [REDACTED]

[REDACTED]

[REDACTED]

[REDACTED]

[REDACTED]	[REDACTED]

2.3 Intended User

The EuGeni SARS-CoV-2 Ag RDT is intended to be used by healthcare professionals which must be qualified and trained. This test is intended for use at the Point of Care (POC) and laboratory settings.

2.4 Mechanism of action of the Device Under Investigation

The EuGeni SARS-CoV-2 Ag RDT is a test strip based on lateral flow technology [REDACTED]
[REDACTED]
[REDACTED] for detection but not differentiation of SARS-CoV and SARS-CoV-2 antigen, and
for internal assay control. [REDACTED]
[REDACTED]

The test line contains an immobilized monoclonal mouse antibody to capture SARS-CoV-2 antigen and the control line contains an immobilized control anti-mouse antibody.

- [REDACTED]
[REDACTED]
[REDACTED]
- [REDACTED]
[REDACTED]
[REDACTED]

[REDACTED] The control line must be detected by the [REDACTED]
[REDACTED] for the test to be valid. If the control line is not detected, the test is considered invalid and must be repeated using another test cassette.

For more precise information on the device description and the reader, please refer to the IFU.

2.5 Device Handling

All investigational products shall be stored according to the labeling and Instructions for Use (IFU) in a secure area to prevent unauthorized access or use.

[REDACTED]
[REDACTED]
[REDACTED]
[REDACTED]
[REDACTED]
[REDACTED]
[REDACTED]

For further device handling warnings and precautions, please see the details in the IFU.

3. CLINICAL PERFORMANCE STUDY OVERVIEW

3.1 Clinical Performance study Objective

The objective of this clinical performance study (CPS) is to determine the diagnostic accuracy (sensitivity and specificity) of the EuGeni SARS-CoV-2 Antigen Rapid Diagnostic Test in the diagnosis of SARS-CoV-2 in specimens from subjects suspected of COVID-19 disease or with unknown COVID-19 status.

CONFIDENTIAL

4. CLINICAL PERFORMANCE STUDY DESIGN AND PROCEDURES

4.1 Clinical performance study design

This clinical performance study (CPS) is designed as a non-interventional, two-arm, prospective, non-randomized, open-label and multi-center study. The two study arms as defined depending on the specimen collection method:

1. Nasopharyngeal specimen collection for comparison with gold-standard RT-PCR
2. Combined nasal mid-turbinate and throat specimen collection for comparison with gold-standard RT-PCR

The expected minimum number of specimens for this CPS is 1850, divided as follows:

Nasopharyngeal specimen collection:

- 300 positive specimens collected from subjects at different timepoints post onset of symptoms: [REDACTED]
- 120 negative specimens from hospitalized patients
- 505 negative specimens from subjects with respiratory symptoms

Combined nasal mid-turbinate and throat specimen collection:

- 300 positive specimens collected from subjects at different timepoints post onset of symptoms: [REDACTED]
- 120 negative specimens from hospitalized patients
- 505 negative specimens from subjects with respiratory symptoms.

[REDACTED] The estimated numbers for each specimen type are approximate and may vary depending on the natural recruitment at the investigational sites to ensure the correct distribution of sample size requirements.

The study has been designed to involve as little pain, discomfort, fear and any other foreseeable risk as possible for the subjects, and both the risk threshold and the degree of distress are specifically defined in the clinical performance study plan (CPSP) and constantly monitored.

The CPS will be conducted in up to 10 sites in Europe. The primary and secondary endpoints will be evaluated when all specimens have been collected and analyzed. [REDACTED]

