4.3 Measures Taken to Avoid and Minimize Bias

This clinical performance study has been designed to be multicenter in order to minimize bias related to site specific standard of care patient and specimen collection method.

All participants who meet the inclusion and exclusion criteria will be eligible to join the study. Inclusion into the two study arms will not be randomized, however sites will be instructed to consecutively enroll subjects into both arms. Recruitment at each investigational site will be limited to █ of the total sample size.

To avoid bias related to the collection method, all study subjects will have a bilateral swab specimen collection for investigational device analysis and for RT-PCR analysis, for direct comparison within the same subjects.

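### Does a minimum of 1850 specimens, split by RT-PCR result, leave the study short of 300 positives per arm unless positivity is 32.4%?

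*Protocol*

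**What the plan says.** The Protocol summary, in its entry on required specimens, gives "A minimum estimated of 1850 prospective specimens". Section 4.1 repeats the figure: "The expected minimum number of specimens for this CPS is 1850, divided as follows". For each of the two swab arms the list is:

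- "300 positive specimens collected from subjects at different timepoints post onset of symptoms"
- "120 negative specimens from hospitalized patients"
- "505 negative specimens from subjects with respiratory symptoms"

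Section 4.1 then adds: "The estimated numbers for each specimen type are approximate and may vary depending on the natural recruitment at the investigational sites". The same sentence goes on to give the reason: "to ensure the correct distribution of sample size requirements".

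Section 6.1 takes subjects who are suspected cases or of unknown status, and RT-PCR status is not an eligibility criterion in section 6.2. Section 4.2.1 describes consecutive and parallel enrolment into the two arms in place of randomisation. Section 4.3 repeats this: "sites will be instructed to consecutively enroll subjects into both arms".

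Protocol section 8.3 and SAP section 2.4 name the targets of 80% sensitivity and 98% specificity. The rest of both sections is redacted.

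**The concern.** The cells are defined by the reference result, which nobody knows at enrolment. With consecutive enrolment, positivity sets the split between positive and negative specimens. The total is exactly the sum of the cells, with no surplus, and the protocol calls the cell counts approximate. Read quickly, the plan seems to allow recruitment to close at 1850 with whatever number of positives has turned up.

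Sensitivity is a primary endpoint in each arm separately, so too few positives would widen its interval. The alternative would be for sites to pick subjects by known or likely status to fill the positive cell. That would distort the case spectrum and could bias sensitivity.

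**Working it through.** **Inputs.** Per arm: 300 positive, 120 hospitalised negative and 505 symptomatic negative specimens (Protocol 4.1). Sensitivity 80% (Protocol 8.3). The documents give no positivity *p*, so it is varied here as an assumption.

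**The plan's figure.** 300 + 120 + 505 = 925 per arm, and 2 × 925 = 1850. It reproduces exactly.

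**Break-even positivity at exactly 925 per arm.** 300/925 = 32.4%. If the hospitalised negatives are a separate stream, it is 300/(300 + 505) = 300/805 = 37.3% among symptomatic subjects.

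**If recruitment stopped at 925 per arm.** Expected positives are 925*p*, and the 95% half-width is 1.96 × √(0.80 × 0.20/*n*):

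| *p* | positives per arm | half-width (points) |
|---|---|---|
| 10% | 92.5 | 8.2 |
| 15% | 138.75 | 6.7 |
| 20% | 185 | 5.8 |
| 25% | 231.25 | 5.2 |
| 32.4% | 300 | 4.5 |

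At *p* = 300/925, the binomial probability of at least 300 positives in 925 is 0.51 in one arm, or 0.51² = 0.26 in both. These numbers are correct, but each one assumes a stop at 925 per arm.

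**If recruitment continued until both cells were full.** The expected number per arm is the larger of 300/*p* and 625/(1 − *p*), pooling all subjects:

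| *p* | 300/*p* | 625/(1 − *p*) | total, both arms |
|---|---|---|---|
| 10% | 3000 | 695 | 6000 |
| 15% | 2000 | 736 | 4000 |
| 20% | 1500 | 782 | 3000 |
| 25% | 1200 | 834 | 2400 |
| 30% | 1000 | 893 | 2000 |
| 35% | 858 | 962 | 1924 |
| 40% | 750 | 1042 | 2084 |

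With a separate hospitalised stream that supplies its 120 negatives, the total is 2 × (300/*p* + 120) as long as positives are limiting. That gives 3240 at 20%, 2640 at 25% and 2240 at 30%.

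Every total is above 1850. This must be so, because an arm with at least 300 positives and at least 625 negatives has at least 925 specimens, whatever the positivity. So 1850 is the smallest total that can satisfy the cells, which is what a minimum should be. Above 32.4%, the positives are reached and the negatives become limiting.

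**The wording set side by side.**

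- *Cap or floor.* The summary and section 4.1 both call 1850 a minimum. Neither says that recruitment ends there.
- *Specimens or enrolment target.* Both places count required specimens by type. Neither presents 1850 as the number of subjects to be approached.
- *The variation sentence.* Its last clause ties the flexibility to meeting the required distribution. Taken whole, it accepts that cells defined by result cannot be fixed in advance. It does not license closing with an empty cell.
- *Consecutive enrolment.* Sections 4.2.1 and 4.3 use the term for allocation to the swab arms. Continuing to enrol in sequence until each cell is full requires no selection on a known result, so the choice between a shortfall and a selected spectrum is not forced.

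**The case for a change.** The best case for the concern is that the visible text sets no firm floor for positives. The only figure called a minimum is the total. The cell counts are called approximate with no visible limit, and section 4.1 times the analysis by the completion of all specimens, not by a count of positives. A study that closed at 1850 with 185 positives per arm would therefore break no explicit rule in the visible text. The purpose clause states an aim and not a threshold. If strata were filled by quota, the visible text does not say how this would be done without regard to likely status.

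Two parts of this stand. First, 1850 specimens do not by themselves guarantee 300 positives per arm. Second, the visible text states neither an assumed positivity nor a closing rule.

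That does not make an error. Text is blacked out after each of the two lines on positive specimens and just before the variation sentence in section 4.1, in section 6.3 on enrolment, and in the sample size sections of both documents. SAP section 2.7 refers back to an interim analysis that is not visible either, so some text on timing is certainly hidden. A closing rule or an assumed positivity would normally stand in these places. Reading the plan as closing at 1850 regardless of the cells also sets aside the stated purpose of the flexibility.

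**Conclusion.** The concern does not hold. The sum of 1850 and the break-even values of 32.4% and 37.3% are right, but the shortfall requires a stop at 1850 that the visible documents do not contain. Read as written, 1850 is a lower bound on specimens by type. It is consistent with recruiting about 2000 at 30% positivity, 3000 at 20% or 6000 at 10% (pooled subjects), each with 300 positives per arm and a half-width of about 4.5 points at 80% sensitivity.

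This conclusion rests on reading the minimum as a minimum, and on reading the variation sentence together with its purpose. The positivities are assumptions, since the documents give none. Whether 300 positives is itself the right number cannot be checked, because its derivation is redacted.

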4.2 Clinical Performance Study Procedures

The Clinical Performance Study will occur in a single subject visit, and no clinical follow up will be required.

4.2.1 Informed Consent and Specimen collection

Before starting any study-related activity, the subject must have provided the signed informed consent form following the requirements in [Section 6.1.2]. Next, the specimen collection will be performed by professionally trained and qualified healthcare personnel.

CONFIDENTIAL

One bilateral swab will be taken to be analyzed with the device under investigation and another bilateral swab will be taken to be analyzed with the gold-standard RT-PCR. The specimen collection method for EuGeni analysis will be performed using either a combined nasal mid-turbinate and throat swab, or a nasopharyngeal swab, which will determine the inclusion into one of the two study arms. Enrolment into the combined nasal mid-turbinate and throat arm or nasopharyngeal will not be randomized, however consecutive and parallel enrollment in both arms will take place. Regardless of the study arm, the RT-PCR specimen collection will always occur to allow result comparison between the investigational device and RT-PCR.

For further information on specimen collection, please refer to IFU [REDACTED]

[figure not shown]
4.2.2 Specimen analysis procedure

The specimen analysis shall be performed by professional healthcare personnel. Specimens to be analyzed by the gold-standard RT-PCR shall follow the procedures established by the standard of care. [REDACTED]

Those specimens analyzed by the EuGeni SARS-CoV-2 Antigen Rapid Diagnostic Test shall follow the procedures laid down in the IFU and protocol. [REDACTED]

- a) Positive results indicate the presence of SARS-CoV-2-antigen and is indicative of primary SARS-CoV-2 infection. [REDACTED]
- b) Negative results indicate the specimen does not contain SARS-CoV-2 antigen. In this case, only the [REDACTED] control line will be displayed. Negative results should be treated as presumptive and should not be used as the sole basis for clinical diagnosis and treatment. [REDACTED]
- c) If a test is Invalid, a new test should be performed with a new subject specimen and a new cassette. [REDACTED]

For more information on the interpretation of results, please refer to the EuGeni SARS-CoV-2 Antigen Rapid Diagnostic Test IFU.

All results obtained from the investigational device should only be noted in the Case Report Form. These results will not impact or drive patient management decisions. The gold-standard RT-PCR results will provide this information to the healthcare professionals and the enrolled subjects.

4.2.2.1 Specimen handling and storage

Study site personnel shall ensure proper storage of specimens in accordance with the IFU.

The study will use fresh human specimens, potentially containing active virus and infectious materials. The handling of samples will be conducted in accordance with standard laboratory containment procedures and following local government guidance for handling SARS-CoV-2 and SARS-CoV-2 containing material.

CONFIDENTIAL

4.3 Measures Taken to Avoid and Minimize Bias

This clinical performance study has been designed to be multicenter in order to minimize bias related to site specific standard of care patient and specimen collection method.

All participants who meet the inclusion and exclusion criteria will be eligible to join the study. Inclusion into the two study arms will not be randomized, however sites will be instructed to consecutively enroll subjects into both arms. Recruitment at each investigational site will be limited to █ of the total sample size.

To avoid bias related to the collection method, all study subjects will have a bilateral swab specimen collection for investigational device analysis and for RT-PCR analysis, for direct comparison within the same subjects.

5. ENDPOINTS

5.1 Primary Endpoints

The primary endpoint of this clinical performance study is to assess the EuGeni SARS-CoV-2 Ag RDT diagnostic accuracy in terms of sensitivity and specificity measured as the following:

- The diagnostic sensitivity of EuGeni SARS-CoV-2 Ag RDT, defined as the ability to identify the presence of a target marker associated with SARS-CoV-2, of nasopharyngeal specimens and combined nasal mid-turbinate and throat specimens, respectively, compared with gold-standard SARS-CoV-2 RT-PCR.
- The diagnostic specificity of EuGeni SARS-CoV-2 Ag RDT, defined as the ability to recognise the absence of a target marker associated with SARS CoV-2, of nasopharyngeal specimens and combined nasal mid-turbinate and throat specimens, respectively, compared with gold-standard SARS-CoV-2 RT-PCR.

